9.4.2 ANALYSIS OF THE PRIMARY EFFICACY ENDPOINT(S)

Blood counts, serum chemistry, urinalysis, ECGs, vital signs, and PTT/INR for the study cohorts will be reported as a mean \pm SD at each of the timepoints listed in the **SoA, Section 1.3**. An analysis of covariance (ANCOVA) to compare the cohorts after adjusting for "baseline" (the adjustment covariate) will be completed. Analysis will be performed in individual subjects to identify changes in safety measurements relative to baseline, and between cohorts at the timepoints listed in the **SoA, Section 1.3** to identify any potential dose-response relationships.

9.4.3 ANALYSIS OF THE SECONDARY ENDPOINT(S)

For the secondary endpoint of RNA sequencing, statistical analysis will be used to detect differential expressed genes (DEGs). Analysis will be performed in individual subjects to identify DEGs relative to baseline, and between cohorts at the timepoints listed in the **SoA, Section 1.3** to identify dose-response relationships.

RNA samples will be sequenced using an Illumina HiSeq approach that will produce 20-30 million paired end reads per sample. Raw reads will be mapped to the human genome. Reads will be normalized as fragments per kilobase million (FPKM) and used to identify DEGs for biomarker evaluation.

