8. Vital signs to be obtained within 1 hour prior to administration of BIO 300 Oral Powder and then approximately 30 minutes, 1, 2, 4, 6, 8, and 12 h following administration of BIO 300 Oral Powder
9. ECGs to be obtained within 1 h prior to BIO 300 Oral Powder administration and then approximately 1, 2, and 4 h following BIO 300 Oral Powder administration
10. Samples for PK assessment to be obtained just prior to BIO 300 Oral Powder administration and then 30 minutes, 1, 2, 4, 6, 8, and 12 h following BIO 300 Oral Powder administration. The time of the blood draw will be ± 10 minutes of the nominal time.
11. Samples for PK assessment to be obtained 24 ± 2 h following administration of BIO 300 Oral Powder
12. Samples for PK assessment to be obtained 48 ± 4 h following administration of BIO 300 Oral Powder
13. Samples for PK assessment to be obtained just prior to administration of BIO 300 Oral Powder and then 30 minutes, 1, 2, and 4 h following BIO 300 Oral Powder administration. The time of the blood draw will be ± 10 minutes of the nominal time.
14. Samples for PD assessment to be obtained -2 to 0 h before BIO 300 Oral Powder administration, and 1, 2, and 4 h following BIO 300 Oral Powder administration. The time of the blood draw will be ± 10 minutes of the nominal time.
15. Samples for PD assessment to be obtained 24 ± 2 h following administration of BIO 300 Oral Powder
16. Samples for PD assessment to be -2 to 0 h before BIO 300 Oral Powder administration, and 4, 8, and 12 h following BIO 300 Oral Powder administration. The time of the blood draw will be ± 10 minutes of the nominal time.
17. Vital signs to be obtained within 1 hour prior to administration of BIO 300 Oral Powder and then approximately 30 minutes, 1, 2, and 4 h following administration of BIO 300 Oral Powder

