9 STATISTICAL CONSIDERATIONS

9.1 STATISTICAL HYPOTHESES

Data analysis of the primary endpoints will be based on measurements of genistein aglycone (free genistein) serum concentrations (0-48 h). They will also be based on safety assessments which include blood counts, serum chemistries, urinalysis, ECGs, vital signs, and PTT/INR at the timepoints listed in the **SoA, Section 1.3**. “Baseline” will refer to measurements taken during the screening visit. If no “baseline” data exists from a parameter, then changes in the parameter time regression will be compared.

As this is a single dose escalation and multiple single dose trial evaluating the safety and pharmacokinetic profile of BIO 300 Oral Powder, the statistical hypotheses for the safety measurements is that there will be no change in safety measurements during BIO 300 Oral Powder dosing, and 7 days after the last BIO 300 Oral Powder dose.

For the secondary endpoint, the statistical hypothesis is that there will be a significant change in the level of expression of one or more genes that is attributable to BIO 300 Oral Powder dose.

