9.4 STATISTICAL ANALYSES

9.4.1 GENERAL APPROACH

An independent statistician using standard statistical techniques will determine statistically significant differences in the trial measurement data. Statistical significance will be set at the nominal level of $p<0.05$. Plasma concentrations (genistein aglycone; free genistein) will be measured (AUC, C_{max} , T_{max} , $T_{1/2}$) and plasma kinetic rate will be calculated using standard procedures and statistical analyses (e.g., AUC using the linear trapezoidal formula and $T_{1/2}$ using linear regression). Data will be summarized by descriptive statistics (mean/medians and standard errors/confidence intervals for continuous response variables and distribution tables or histograms for discrete response variables).

Baseline characteristics will be compared using matched-pair t-tests. The computed change from baseline will be calculated for all measured variables and expressed as the mean change from baseline

and accompanying standard deviation (SD) of the change from baseline. Repeated measures ANOVA tests will be used to compare changes in scores for each variable between each treatment group. Matched pair t-tests will be used to compare the change scores within each treatment group. All data analyses will be conducted on the subjects who completed the study treatment periods and statistical significance will be set at $p<0.05$.

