9.3. Analysis for Blood-Based Biomarkers

Blood-based biomarkers will be identified by extracting RNA from whole blood samples and performing transcriptome analysis to determine differential gene expression. Transcriptome analysis will be conducted by paired-end RNA sequencing. After investigating the quality of the raw sequencing data, sequence reads will be trimmed to remove possible adapter sequences and nucleotides with poor quality using Trimmomatic v.0.36. The trimmed reads will be mapped to the Homo sapiens reference genome available on ENSEMBL using the STAR aligner v.2.5.2b. The STAR aligner is a splice aligner that detects splice junctions and incorporates them to help align the entire read sequences. Binary Alignment Map (BAM) files will be generated as a result of this step. Unique gene hit counts will be calculated by using feature counts from the Subread package v.1.5.2. Only unique reads that fell within exon regions will be counted.

After extraction of gene hit counts, the gene hit counts table will be used for downstream differential expression analysis. Using DESeq2, a comparison of gene expression between the groups of samples will be performed. The Wald test will be used to generate p-values and Log2 fold changes. Genes with adjusted p-values < 0.05 and absolute log2 fold changes > 1 will be called as differentially expressed genes for each comparison. A gene ontology analysis will be performed on the statistically significant set of genes by implementing the software GeneSCF. The goa_human GO list will be used to cluster the set of genes based on their biological process and determine their statistical significance. A principal component analysis (PCA) will be performed using the "plotPCA" function within the DESeq2 R package. This plot will show the samples in a 2D plane spanned by their first two principal components. The top 500 genes, selected by highest row variance, will be used to generate the plot.

10. Safety Analyses

Summaries of safety endpoints will include data collected from the safety analysis dataset. Relevant data supporting safety analyses will be listed by subject.

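### Protocol 9.4.3 and SAP 9.3 give unreconciled methods for calling differentially expressed genes; a literal single-subject call has no error degrees of freedom, and the RNA baseline is undefined.

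*Combined protocol and SAP*

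**What the plan says.** Protocol 9.1 states the secondary hypothesis: "there will be a significant change in the level of expression of one or more genes that is attributable to BIO 300 Oral Powder dose". Protocol 9.4.3 plans the gene search at two levels: "Analysis will be performed in individual subjects to identify DEGs relative to baseline", and also between cohorts at the timepoints in the Schedule of Activities. On the expression measure it says: "Reads will be normalized as fragments per kilobase million (FPKM) and used to identify DEGs for biomarker evaluation". That section names no test, fold-change cut or adjustment across genes. The only threshold is the general one in 9.4.1: "Statistical significance will be set at the nominal level of" p < 0.05.

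SAP 9.3 describes another procedure: "the gene hit counts table will be used for downstream differential expression analysis". It continues: "Using DESeq2, a comparison of gene expression between the groups of samples will be performed". A Wald test follows, and a gene is called if its adjusted p-value is below 0.05 and its absolute log2 fold change is above 1. SAP 9.3 mentions neither FPKM nor a subject-by-subject analysis. It does not say what the groups are, whether samples are paired by subject, or which adjustment is used.

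Sampling is in Schedule of Activities notes 14 to 16. Note 14 reads: "Samples for PD assessment to be obtained -2 to 0 h before BIO 300 Oral Powder administration, and 1, 2, and 4 h following" dosing. Note 15 adds one draw at 24 h. Protocol 9.1 and SAP 7.1 both place baseline at the screening visit, where the Schedule has no RNA sample.

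**The concern.** Three things leave the gene list undetermined.

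- **Unit of analysis.** A gene call within one subject at one timepoint has no replication. A p-value for it needs a variance brought in from outside the comparison, and the plan supplies none.
- **Expression measure and rule.** FPKM with a nominal 0.05 and counts with an adjusted p-value plus a fold-change cut are different procedures. The list depends on which document the analyst follows, and neither says which governs.
- **Reference sample.** Change from baseline cannot be computed for RNA if baseline means screening.

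The stakes are more than tidiness. Protocol section 3 justifies the biomarker endpoint by its role in approval under the FDA Animal Rule, and a secondary objective combines PK and PD to identify a putative human efficacious dose. A list whose method can be settled after the data are seen is weak support for either.

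**Working it through.** **1. The plan's own figures.** Completers: 4 × 6 + 8 = 32, as stated in SAP section 4. RNA blood volume: 5 mL × 5 draws = 25 mL (single dose) and 5 mL × 9 draws = 45 mL (multiple dose), matching protocol 8.3.1 and 8.3.2. So there is one draw per subject per timepoint. Protocol 8.3 lists two PAXgene tubes, but two tubes from one draw are at most technical replicates. The documents give no power, effect size or dispersion for the RNA endpoint.

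**2. Residual degrees of freedom.** Two groups of samples: df = samples − 2. Pairs by subject: df = n − 1.

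| Comparison | df |
|---|---|
| One subject, pre-dose v one post-dose sample | 1 + 1 − 2 = 0 |
| Cohort, paired by subject, n = 6 | 6 − 1 = 5 |
| Cohort, paired by subject, n = 8 | 8 − 1 = 7 |
| Cohort, unpaired, 6 v 6 | 12 − 2 = 10 |
| Cohort, unpaired, 8 v 8 | 16 − 2 = 14 |

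The unpaired rows have more df only because they treat two samples from one person as independent and leave between-subject variation in the error.

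Counted against Day 1 pre-dose, the single-subject contrasts number 24 × 4 + 8 × 8 = 96 + 64 = 160.

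**3. What an imported variance would do (illustration; inputs assumed).** Suppose a one-against-one test takes its variance from Poisson noise alone. Simulated rejection of null genes at nominal 0.05, for mean counts of 50, 200 and 1,000:

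| Assumed extra-Poisson CV | 50 | 200 | 1,000 |
|---|---|---|---|
| 0 | 0.051 | 0.051 | 0.050 |
| 0.1 | 0.109 | 0.256 | 0.553 |
| 0.2 | 0.255 | 0.512 | 0.760 |

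**4. What a bare fold-change cut would do (illustration; a rule that neither document states).** If the log2 value of one sample has SD s, the difference of two has SD s√2, and P(|d| > 1) = 2[1 − Φ(1/(s√2))]. For an assumed 15,000 genes:

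| Assumed s | Probability | Null genes flagged per contrast |
|---|---|---|
| 0.2 | 0.0004 | about 6 |
| 0.3 | 0.0184 | about 276 |
| 0.4 | 0.0771 | about 1,156 |
| 0.5 | 0.157 | about 2,359 |

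**5. FPKM across replicate subjects (simulation; inputs assumed).** Gene length cancels within a gene, so depth normalisation stands in for FPKM. Assumed: mean count 500, within-subject CV 0.2, paired t-test on log2 values. If a share of reads moves to other genes after dosing, every unchanged gene shifts by log2(1 − share); a 10% share gives log2(0.9) = −0.152.

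| Share of reads shifted | Null rejection, n = 6 | Null rejection, n = 8 |
|---|---|---|
| 0 | 0.050 | 0.050 |
| 5% | 0.065 | 0.072 |
| 10% | 0.114 | 0.140 |
| 20% | 0.327 | 0.456 |

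The test holds its level when RNA composition is stable and loses it as composition shifts.

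**6. Threshold.** At an unadjusted 0.05, an assumed 10,000 to 20,000 null genes give 500 to 1,000 calls per comparison (0.05 × 10,000; 0.05 × 20,000). The SAP's adjusted p-value is there to control this; protocol 9.4.3 has no counterpart.

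**7. Baseline.** The Schedule and both blood-volume tables show no PD draw at screening. The first RNA sample is taken within the 2 h before the Day 1 dose.

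**The case against.** The strongest defence is that the subject-level clause is ambiguous. Protocol 9.4.2 uses nearly the same wording for safety data, and 9.4.1 tests within-group change with matched-pair t-tests. Within-subject change pooled across subjects is therefore a fair reading, and it has 5 or 7 df. Protocol 9.1 also gives a fallback where no baseline exists, a regression on time; a straight line through 5 or 9 samples would leave 3 or 7 df. This stands in part: zero df belongs to the literal reading only. But serial samples from one person are weak replicates, and the pooled reading still lacks a pairing term and defined groups in SAP 9.3. The clause needs correcting either way.

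A reader might also infer more than the documents support:

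- **That FPKM cannot give a valid test.** It can across subjects, as step 5 shows with stable composition. Its faults are composition bias and its mismatch with the SAP's count model.
- **That the SAP's cohort-level analysis replaces a purely single-subject protocol plan.** The protocol sentence also plans between-cohort comparisons, and the SAP speaks only of groups of samples, which could be cohorts, timepoints or both.
- **That two incompatible gene lists are promised.** Neither document promises two lists, and the lists could overlap.
- **That per-subject lists would be mostly noise.** This needs the number of truly changed genes, which is not given. The figures in step 4 also drop the SAP's adjusted p-value and run from about 6 to about 2,359 with the assumed SD.

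**Conclusion.** The concern holds as an unreconciled specification. The two documents differ in expression measure, unit of analysis and threshold, and neither takes precedence. On the literal reading, each of the 160 single-subject contrasts has 0 residual df and cannot give a valid p-value. The SAP's own comparison is also indeterminate, because its groups and pairing are not stated, and baseline for RNA points to a visit with no RNA sample.

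The df results, the 160 contrasts and the baseline gap follow from the documents, taking Day 1 pre-dose as the reference for the count of 160. The chance-call and rejection rates are illustrations under assumed SDs, CVs, mean counts, gene numbers and composition shifts; they show direction, not expected size. The change should be made, but it does not touch the primary safety and PK endpoints.

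**What to change.** In protocol 9.4.3, state that:
- log2 changes from Day 1 pre-dose in individual subjects are listed descriptively only;
- differentially expressed genes are called only across subjects, from the SAP count model on raw gene counts with size-factor normalisation;
- FPKM is for display only.

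In SAP 9.3:
- define the contrasts: each post-dose time against Day 1 pre-dose within cohort, and between cohorts, saying whether the latter compares levels at a time or changes from pre-dose;
- include subject as a pairing factor for the within-cohort contrasts;
- set Day 1 pre-dose as the RNA baseline, as an exception to SAP 7.1 and protocol 9.1;
- name the p-value adjustment method.

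The cost is a few sentences in each document and no new assays or visits. The SAP cites protocol version 1.0 and undertakes to review later amendments. Version 2.0 changed the Day 6 PD draw times, so a review is due in any case. The synopsis places sequencing after all phase 1 studies are complete; on that schedule the text can be settled before any gene list exists.

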9.4.4 SAFETY ANALYSES

All adverse events (AEs), including clinically significant laboratory abnormalities, will be collected in the site's source document, and reported on the AE case report form (CRF). Documentation of the serious event will be reported on the Serious Adverse Event (SAE) CRF and submitted to the Sponsor within 24 hours of awareness.

AEs will be identified using the FDA Guidance for Industry Toxicity Grading Scale for Healthy Adult and Adolescent Volunteers Enrolled in Preventive Vaccine Clinical Trials. The following information regarding each adverse event will be recorded:

- Assessment period
- Severity Grade (0-4)
- Attribution to study agent (relatedness)
- Date AE occurred
- Date AE resolved
- Whether or not the event was reported as an SAE
- Whether or not the participant dropped due to the event
- Action taken with study agent
- Outcome of the event
- Additional investigator comments

AEs will be summarized by study group and system organ class. Tables will include summaries of all AEs, all SAEs, all BIO 300 Oral Powder related AEs, all BIO 300 Oral Powder related SAEs, all Grade 3 or 4 AEs, and all AEs leading to death or study discontinuation.

9.4.5 BASELINE DESCRIPTIVE STATISTICS

Baseline characteristics, such as subject age, vital signs, laboratory results, and BMI will be compared between the dosing cohorts using descriptive statistics. ANOVA analysis will be used to compare each parameter between the study cohorts at baseline.

9.4.6 PLANNED INTERIM ANALYSES

Following the 2000 mg single ascending dose cohort, safety and PK analysis will be completed to determine the dose for the final cohort of the single ascending dose study.

9.4.7 SUB-GROUP ANALYSES

No sub-group analysis is planned.

9.4.8 TABULATION OF INDIVIDUAL PARTICIPANT DATA

All individual participant data will be listed by measure and timepoint.

9.4.9 EXPLORATORY ANALYSES

There are no exploratory analyses planned for this study.

10 SUPPORTING DOCUMENTATION AND OPERATIONAL CONSIDERATIONS

10.1 REGULATORY, ETHICAL, AND STUDY OVERSIGHT CONSIDERATIONS

10.1.1 INFORMED CONSENT PROCESS

10.1.1.1 CONSENT/ASSENT AND OTHER INFORMATIONAL DOCUMENTS PROVIDED TO PARTICIPANTS

Consent forms describing in detail the study intervention, study procedures, and risks are given to the participant and written documentation of informed consent is required prior to starting intervention/administering study intervention. The informed consent form (ICF) is submitted with this protocol.

10.1.1.2 CONSENT PROCEDURES AND DOCUMENTATION

The environment where the process of consent is conducted will be private, confidential, and safe in order to facilitate a constructive dialogue between the prospective subject and the person(s) involved in obtaining consent. All prospective subjects must have the cognitive ability to provide legally effective informed consent. Individuals who do not have such ability (i.e., decisionally impaired persons) can only be enrolled in research through consent of their legally authorized representative (LAR). If there is any concern about an individual's cognitive ability an appropriate assessment should be performed by a qualified individual.

The informed consent will be presented and discussed with the prospective subject in a sequential manner utilizing the approved ICF as a guide. The presentation should be structured to facilitate a dialogue with reinforcement and elaboration of important information (e.g., the risks of the research). The person(s) involved in obtaining the subject's consent will constantly evaluate whether the process is

achieving the goal which is obtainment of legally effective informed consent from the subject. In addition to paying attention to general signs of information receptivity, the person obtaining consent may ask open-ended questions in order to identify points of confusion which require clarification.

A delayed consent procedure will be used in order to afford the subject the opportunity to discuss participation in the research with family, friends, counselors, or other confidants before they sign the ICF. If the individual is uncomfortable or anxious about participating in the research, they will be instructed to take the ICF home for further review and consideration before deciding whether or not to participate in the research.

The informed consent process will be documented by personnel qualified to attest that the subject has provided legally effective informed consent. The individual documenting the process and the consenting subject will sign and date the ICF and indicate the time at which the ICF was signed. It is unacceptable for the person documenting consent to sign the ICF in advance of obtaining the subject's signature.

The informed consent document must be reviewed and approved by the IRB, any changes to the informed consent must be submitted to the IRB for approval prior to initiation.

10.1.2 STUDY DISCONTINUATION AND CLOSURE

This study may be temporarily suspended or prematurely terminated if there is sufficient reasonable cause. Written notification, documenting the reason for study suspension or termination, will be provided by the suspending, or terminating party to study participants, Principal Investigator, funding agency, the Investigational New Drug (IND) Sponsor and regulatory authorities. If the study is prematurely terminated or suspended, the Principal Investigator (PI) will promptly inform study participants, the Institutional Review Board (IRB), and Sponsor and will provide the reason(s) for the termination or suspension. Study participants will be contacted, as applicable, and be informed of changes to study visit schedule.

Circumstances that may warrant termination or suspension include, but are not limited to:

- Determination of unexpected, significant, or unacceptable risk to participants
- Demonstration of efficacy that would warrant stopping
- Insufficient compliance to protocol requirements
- Data that are not sufficiently complete and/or evaluable
- Determination that the primary endpoint has been met
- Determination of futility

Study may resume once concerns about safety, protocol compliance, and data quality are addressed, and satisfy the Sponsor, IRB and/or Food and Drug Administration (FDA).

10.1.3 CONFIDENTIALITY AND PRIVACY

In order to maintain subject confidentiality, a subject number and initials will identify all study subjects on CRFs and other documentation submitted to the Sponsor.

Participant confidentiality and privacy is strictly held in trust by the Principal Investigator, their staff, and the Sponsor(s) and their interventions. This confidentiality is extended to cover all aspects of the clinical information relating to participants. Therefore, the study protocol, documentation, data, and all other

information generated will be held in strict confidence. No information concerning the study, or the data will be released to any unauthorized third party without prior written approval of the Sponsor.

All research activities will be conducted in as private a setting as possible.

The study monitor, other authorized representatives of the Sponsor, representatives of the Institutional Review Board (IRB), regulatory agencies may inspect all documents and records required to be maintained by the investigator, including but not limited to, medical records (office, clinic, or hospital) and pharmacy records for the participants in this study. The clinical study site will permit access to such records.

The study participant's contact information will be securely stored at each clinical site for internal use during the study. At the end of the study, all records will continue to be kept in a secure location for as long a period as dictated by the reviewing IRB, Institutional policies, or Sponsor requirements.

Study participant research data, which is for purposes of statistical analysis and scientific reporting, will be transmitted to and stored at a site designated by the Sponsor. This will not include the participant's contact or identifying information. Rather, individual participants and their research data will be identified by a unique study identification number. The study data entry and study management systems used by clinical sites staff will be secured and password protected. At the end of the study, all study databases will be de-identified and archived at the Sponsor's designated site.

